4.4 Exclusion criteria

Babies with life threatening congenital malformations

4.5 Withdrawal criteria

Given the observational nature of this study and the lack of risks to the health of the baby, withdrawal should occur only upon parental request.

4.6 Sample collection and processing

All samples should be collected in pre-assembled sample collection packs containing a PAXgene bottle (for gene expression) and 2 EDTA bottles (for epigenetics and CNVs) with printed barcodes. The sample collection packs will be provided to all recruiting centres.

Genomic Imaging in Neonatal Encephalopathy

A total of approximately half a teaspoon (3 ml) of blood will be collected by venepuncture during blood sampling for routine clinical care or via indwelling arterial catheter, into 2 EDTA bottles and 1 PAXgene bottle by local clinicians/nurses, within 6 hours of birth from all recruited babies. In addition, 5ml of blood will be collected by venepuncture from each parent into EDTA bottles by local clinicians/nurses/phlebotomists or research nurses, wherever possible. This will allow us to examine the proportion of CNVs that are genetically transmitted in comparison to de novo mutations. The collected blood samples will be labelled using pre-printed barcodes (anonymised using the study number and date/time of collection) and will be transported to Imperial College London for analysis in batches.

Details of antenatal and postnatal events, and other routine clinical and imaging data will be collected. We will also obtain relevant clinical data from the participants' (baby and mother) medical records or from GPs/local hospitals if needed (GPs will be informed of study participation unless otherwise requested by parents). We will also collect the 3 Tesla MR data that is acquired as a part of routine clinical care. Parents will be contacted regularly via their preferred method of contact. Study newsletters will be sent to parents, unless they opt out.

4.7 Evaluation of neurological outcomes

All babies will have detailed neurodevelopmental evaluation including Bayley Scales of Infant Development (BSID-III or IV if available), Gross Motor Function Classification System (GMFCS), and hearing and vision assessment between 18 to 24 months of age. Severe disability will be defined as any one of the following: both cognitive and language composite BSID-III scores <70, GMFCS level 3–5, hearing impairment requiring hearing aids, or blindness. Moderate disability will be defined as both cognitive and language composite BSID-III scores between 70 and 84 and one or more of the following: GMFCS level 2, hearing impairment with no need for amplification or a persistent seizure disorder. The outcomes will also be assessed by categorisation of these scores and by including mortality as an outcome. An adverse outcome will be defined as death or, in survivors, moderate or severe disability.

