3. STUDY AIMS

Primary

1. To compare the activity of specific genes in blood (host gene expression) at birth with brain injury on magnetic resonance scans within two weeks of birth, and with neurodisability at two years of age in babies with neonatal encephalopathy

Secondary

1. To identify and characterise the host gene expression pathways associated with basal ganglia/thalamic injury and white matter injury on magnetic resonance scans in neonatal encephalopathy
2. To identify a minimal transcriptomic signature of adverse neurological outcomes
3. To examine the relation of epigenetic changes with brain injury and neurodisability after neonatal encephalopathy
4. To examine the association of copy number variants with brain injury and neurodisability after neonatal encephalopathy

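### The disability definitions in Protocol section 4.7 drop from the adverse group a child with a listed moderate-type impairment, one composite below 70 and the other 70 to 84, while a better-scoring child with the same impairment counts as adverse

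*Protocol*

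**What the plan says.** Protocol section 4.7 builds the two-year outcome in three steps.

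- Severe: "Severe disability will be defined as any one of the following: both cognitive and language composite BSID-III scores <70", or any one of "GMFCS level 3–5, hearing impairment requiring hearing aids, or blindness". Each item is sufficient alone.
- Moderate: "Moderate disability will be defined as both cognitive and language composite BSID-III scores between 70 and 84 and one or more of the following". The score condition and a further impairment are both needed, and the list of further impairments has three entries: "GMFCS level 2, hearing impairment with no need for amplification or a persistent seizure disorder".
- Adverse: "An adverse outcome will be defined as death or, in survivors, moderate or severe disability".

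The section adds that "The outcomes will also be assessed by categorisation of these scores and by including mortality as an outcome", without giving cut-points. The primary aim in section 3 compares gene expression with MR brain injury and "with neurodisability at two years of age in babies with neonatal encephalopathy". Section 5.1 uses adverse versus normal outcome as one of its sizing contrasts, and section 5 judges the signature by AUC, sensitivity and specificity.

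**The concern.** Each score condition applies to both composites at once, and the moderate band has a floor of 70. A child whose scores fall on either side of 70 is too low on one composite for moderate and too high on the other for severe. If that child also has a moderate-type impairment, the rule ranks the child as better than one with the same impairment and higher scores. A severity rule should never improve a child's class because a score fell.

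At stake is the binary outcome behind the two-year part of the primary aim and behind the outcome signature. Impaired children labelled not adverse contaminate the comparison group, which would be expected to weaken the adverse-versus-normal expression contrast. They also corrupt the reference standard: if the signature correctly flags such a child, the flag is scored as a false positive.

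**Working it through.** **Where the definition enters the plan's figures.** Section 5.1 assumes 50% adverse among 272 evaluable babies: 0.50 × 272 = 136, as stated. The remaining 272 − 136 = 136 are by implication the comparators. Nothing below depends on these figures.

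**Rules as written**, with C = cognitive and L = language composite:

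- Severe = (C < 70 and L < 70), or GMFCS 3–5, or hearing aids, or blindness.
- Moderate = (70 ≤ C ≤ 84 and 70 ≤ L ≤ 84) and (GMFCS 2, or unaided hearing impairment, or seizures).
- Adverse in survivors = severe or moderate.

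**Enumeration**, for survivors with no GMFCS 3–5, hearing aids or blindness. The result is the same if C and L are swapped.

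| One composite / the other | No further impairment | At least one moderate-type impairment |
|---|---|---|
| <70 / <70 | severe | severe |
| <70 / 70–84 | not adverse | **not adverse** |
| 70–84 / 70–84 | not adverse | moderate |
| <70 / ≥85 | not adverse | not adverse |
| 70–84 / ≥85 | not adverse | not adverse |
| ≥85 / ≥85 | not adverse | not adverse |

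The cell in bold is the fault. With GMFCS 2 held fixed:

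- 75/75: moderate, so adverse.
- 65/75: not severe because 75 is not below 70, and not moderate because 65 is not in 70–84, so not adverse.
- 65/65: severe, so adverse.

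The result is the same with unaided hearing impairment, with seizures, or with all three together.

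**Where the order is not broken.**

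- Without a further impairment, 75/75 and 65/75 are both not adverse.
- With GMFCS 3–5, hearing aids or blindness, every score combination is severe.
- With one composite at 85 or above and no severe criterion, no child with the same impairment who scores as high or higher on both composites is adverse. This is a strict rule but a consistent one.

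**Possible size.** The protocol gives no mean, SD or correlation for the composites. Assume bivariate normal scores rounded to integers, SD 15 and a common mean. The share of survivors with one composite below 70 and the other in 70–84 is then:

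| Mean | r = 0.5 | r = 0.7 | r = 0.85 |
|---|---|---|---|
| 80 | 18.3% | 16.5% | 13.3% |
| 85 | 12.4% | 11.8% | 9.7% |
| 90 | 7.3% | 7.4% | 6.3% |
| 95 | 3.8% | 4.2% | 3.7% |

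That is about 4% to 18%, and it is a ceiling. The misclassified share is this share multiplied by f, the fraction of these children who have a moderate-type impairment and no severe criterion. The protocol gives no f. Purely for illustration, f of 10% to 30% gives 0.037 × 0.10 = 0.4% up to 0.183 × 0.30 = 5.5% of survivors.

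**The case against.** The best defence is that few children are involved and that the scores will also be analysed in categories, so low scores are not lost. Both parts have some force. The number may be small. The categorised analysis, however, is an addition without stated cut-points, and it leaves the definition of adverse outcome as it stands. No other section assigns the missing combination. Nor is this a detail left to a statistical analysis plan: the protocol fixes the definition, so a plan that follows it inherits the fault and a plan that departs from it contradicts the protocol.

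A reader might infer more than the text supports:

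- **That every child straddling 70 is misclassified.** Those with GMFCS 3–5, hearing aids or blindness are already severe. Those with no further impairment are treated like a 75/75 child with none.
- **That all expression contrasts are diluted.** The contrasts of white matter or basal ganglia injury with normal MR do not use the disability definition.
- **That the adverse share will fall below the planned 50%.** Section 5.1 takes 50% from preliminary data and does not say which definition produced it. If it was this one, there is no shortfall.
- **That a head count can be given.** The protocol states neither the number of survivors nor the distribution of scores.

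Two limits also stand. Section 4.7 does not define the normal-outcome group of section 5.1; that the affected children join it is inferred from the 136 of 272. Section 4.7 also permits "Bayley Scales of Infant Development (BSID-III or IV if available") while stating its cut-offs for BSID-III only, but that is a separate wording matter and this point does not rest on it.

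**Conclusion.** The point holds in a narrow form. Section 4.7 breaks the order of severity for survivors who have one composite below 70 and the other in 70–84, at least one listed moderate-type impairment, and no non-score severe criterion. This follows from the text alone and needs no assumption. It affects the two-year adverse-versus-normal comparison and the AUC, sensitivity and specificity of the outcome signature.

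The size is unknown. The 4% to 18% of survivors is an upper bound resting on assumed score distributions, and only an unstated fraction of it is misclassified. The direction of the effect on the expression contrast, towards attenuation, is an expectation and not a calculated result. The correction is worth making because the fault lies in an outcome within the primary aim and costs almost nothing to remove now.

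**What to change.** Reword moderate disability in section 4.7 so that it applies to a survivor who does not meet severe disability, has both cognitive and language composites below 85, and has at least one of "GMFCS level 2, hearing impairment with no need for amplification or a persistent seizure disorder".

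This keeps the protocol's own cut-offs and its list of impairments. The only children whose adverse status changes are those in the bold cell of the table, who become moderate. The order is then consistent: with GMFCS 2, 75/75, 65/75 and 65/65 are all adverse. Combinations with one composite at 85 or above remain not adverse, as now.

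The cost is one sentence in an amendment and no new data. The adverse proportion rises slightly compared with literal use of the present wording. The amendment should be in place before any outcome data are examined. Section 9 defers the primary outcomes to the end of follow-up but allows secondary outcomes, among which section 3 lists the signature of adverse outcome, to be examined once recruitment ends. The earlier of these dates is the safe deadline; a later change would be open to the charge of being post hoc.

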5. STATISTICS AND DATA ANALYSIS

Statistical analysis will be performed using R (version 3.3.2). In order to identify lists of differentially expressed transcripts between the patient groups for biological interpretation, we will fit linear regression models and calculate moderated t statistics for each transcript. The p values will be corrected for multiple testing using the Benjamini-Hochberg false discovery rate method to control for type I errors. We will use computational network-based approaches to unravel the underlying biological processes, which produce the gene expression measurements. IPA (<http://www.ingenuity.com>), DAVID, and a manually curated data set of human gene interactions in InnateDB (<http://www.innatedb.com>) will be used to examine biological network relationships and any associations with known pathways. To identify signatures of differentially expressed transcripts with diagnostic potential, we will apply variable selection methods to the significantly differentially expressed transcripts using the disease risk score, and its predictive accuracy will be calculated using the pROC package in R. The area under the receiver operating characteristic curve, sensitivity, and specificity will be assessed.

5.1 Sample size calculation

A total sample size of 272 patients (R (v3.3.1) and RNASeqPower (v1.12.0): 108 babies with WM injury, 82 with BGT injury, 82 with normal MR scans and 136 babies with adverse outcome) is required, based on the following assumptions supported by our preliminary data:

(i) RNA-sequencing depth of at least 30 million of reads (ii) Variance of 1.01 between encephalopathic babies with adverse outcomes and those with a normal outcome (iii) Variance of 0.9 between encephalopathic babies with normal MR scans and those with WM injury, and 0.78 between encephalopathic babies with normal MR scans and those with basal ganglia injury (iv) Type I error rate of 0.05 and Type II error rate of 0.1 (90% power). Our preliminary data suggest WM injury in 40%, basal ganglia injury in 30 %, normal MR scans in 30%, and a 50% with an adverse outcome.

Genomic Imaging in Neonatal Encephalopathy

We have increased the total sample size to 300 to accommodate a 10% drop-out rate, and poor MR data quality.

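### Section 5.1 states no fold change and leaves the variability scale unclear; on the best-fitting reading, white-matter versus normal MR has about 85% power, not 90%

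*Protocol*

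**What the plan says.** Protocol section 5.1 gives the requirement as "A total sample size of 272 patients", broken down as "108 babies with WM injury, 82 with BGT injury, 82 with normal MR scans and 136 babies with adverse outcome". The calculation was done in R with the RNASeqPower package. The printed assumptions are:

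- "RNA-sequencing depth of at least 30 million of reads";
- "Variance of 1.01 between encephalopathic babies with adverse outcomes and those with a normal outcome";
- "Variance of 0.9 between encephalopathic babies with normal MR scans and those with WM injury";
- "0.78 between encephalopathic babies with normal MR scans and those with basal ganglia injury";
- a type I error rate of 0.05 and 90% power, given once for all comparisons.

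The same section expects WM injury in 40% of babies, basal ganglia/thalamic (BGT) injury in 30%, a normal scan in 30% and an adverse outcome in 50%. Enrolment is raised to 300 for drop-out and poor MR data. The section gives no fold change or other effect size, does not say whether the test is one- or two-sided, and does not say whether the sizes are per-group requirements for equal groups.

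**The concern.** Babies with normal scans are the comparator for both the WM and the BGT contrast. The two contrasts have different variability inputs (0.9 and 0.78), so at a common fold change they need different group sizes. Yet the shared comparator is set at 82, which is also the BGT size. If 108 is the per-group size for WM, that contrast is short of comparators and the single 90% figure does not apply to it. In addition, the inputs are called variances, whereas this software's formula takes a CV. A reader who used the inputs as labelled, with equal groups, would not recover the printed sizes. MR injury is part of the primary aim and WM injury is named in the first secondary aim (section 3), so this contrast matters to the study.

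**Working it through.** **Inputs.** From section 5.1: variability 0.78 (BGT), 0.9 (WM), 1.01 (outcome); alpha 0.05; power 90%; group sizes 82, 108, 82 and 136. Assumed here: two-sided test (z = 1.960 and 1.282), 30 million reads entered as depth 30, and a fold change solved for because none is printed.

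**Formula.** For equal groups, n per group = 2(1.960 + 1.282)² × (1/depth + CV²) / (ln FC)². With depth 30 and FC = 1.5 this is 127.8 × (1/30 + CV²).

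**Reproducing the printed sizes.**

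| Contrast | Input | Printed size | Input read as CV | Input read as variance |
|---|---|---|---|---|
| BGT vs normal MR | 0.78 | 82 | 82.0 | 104.0 |
| WM vs normal MR | 0.9 | 108 | 107.8 | 119.3 |
| Adverse vs normal outcome | 1.01 | 136 | 134.7 | 133.4 |

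On the CV reading, the fold changes implied by the printed sizes are 1.500, 1.499 and 1.497, so a single value of 1.5 serves all three. A plain two-means formula with the inputs as SDs and a difference of about 0.40 fits about as well.

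**A check that needs no fold change.** With equal groups and one common fold change, alpha and power, sizes are proportional to (1/depth + variability term), so only ratios matter.

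| Ratio | Printed sizes | Inputs squared | Inputs as variances |
|---|---|---|---|
| WM / BGT | 108/82 = 1.317 | 0.81/0.6084 = 1.331 | 0.9/0.78 = 1.154 |
| Outcome / WM | 136/108 = 1.259 | 1.0201/0.81 = 1.259 | 1.01/0.9 = 1.122 |
| Outcome / BGT | 136/82 = 1.659 | 1.0201/0.6084 = 1.677 | 1.01/0.78 = 1.295 |

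The depth term only pulls ratios towards 1. Under those conditions the variance reading therefore cannot reach the printed ratios at any depth.

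**Power at the planned sizes (CV reading, 1.5-fold, depth 30).** Power = Φ( ln 1.5 / √[(1/30 + CV²)(1/n₁ + 1/n₂)] − 1.960 ).

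- BGT, 82 vs 82: 90.0%.
- Outcome, 136 vs 136: 90.3%.
- WM, 108 vs 108: 90.05%.
- WM, 108 vs 82 as planned: Φ(3.014 − 1.960) = 85.4%.
- WM, 120 vs 90 (all 300 evaluable at 40% and 30%): Φ(3.166 − 1.960) = 88.6%.

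**Dependence on the fold change.** Take 108 per group as exactly 90%, whatever the fold change. The effective per-group size at 108 vs 82 is 2 × 108 × 82/190 = 93.2, so power is Φ(3.242 × √(93.2/108) − 1.960) = 85.4%. The one-sided version gives 85.9%.

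**Equivalent statements.** At 108 vs 82, the fold change detectable with 90% power is exp(3.242 × √[(1/30 + 0.81)(1/108 + 1/82)]) = 1.55. Reaching 90% at 1.5-fold with a 40:30 split would take 107.8 × 0.7/(2 × 0.4 × 0.3) ≈ 315 evaluable babies.

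**The case against.** The strongest objection is that the reconstruction is not unique. The section never says that 108 is a per-group figure for equal groups, and 272 × 40%, 30% and 50% gives 108.8, 81.6 and 136. The listed sizes could therefore simply be the expected make-up of one cohort of 272. If the inputs are taken as true variances with the unequal groups as printed, at depth 30, the fold change detectable with 90% power is 1.582 for WM (108 vs 82) and 1.579 for BGT (82 vs 82). The two agree closely at other depths as well. At 1.58-fold, power is about 90% for both MR contrasts and 96% for outcome, so there would be no shortfall. It is also fair to say that the CV formula gives 135, not 136, for outcome.

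This arithmetic is correct, and it rules out saying that the inputs can only be CVs or that 85% is established. It is nevertheless the less likely reading. It needs an unstated, non-round fold change and explains 136 only as half of 272. The CV reading comes within about one baby per group of all three sizes at round inputs, with the software the protocol names. Nor does the cohort-composition argument alone rescue the 90%. If 136 per outcome group is what gives 90%, and the same fold change applies throughout, WM power at depth 30 is 85.1% on the CV reading and 81.0% on the variance reading.

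The objection that the effect is modest also stands. The gap is about five points, and it is per-gene power at 0.05, whereas section 5 applies a false discovery rate correction across transcripts.

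**Conclusion.** The point holds in a limited form. Section 5.1 omits the fold change and labels its variability inputs in a way that, with equal groups and one fold change, does not return its own sizes. On the best-fitting reading, WM versus normal MR has about 85% power at the planned 108 vs 82, against the stated 90%. The figure is about 89% if every enrolled baby is evaluable. BGT and outcome keep their 90%.

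This rests on assumptions the protocol does not confirm: inputs on the CV or SD scale, a common 1.5-fold change, reads entered as depth 30, and 108 meant as a per-group size. The 85% itself does not depend on the fold change, but it does depend on 108 vs 108 being the 90% design.

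A reader might infer that the calculation is proven wrong, or that the study must recruit more babies. The documents support neither: the alternative in which both MR contrasts reach 90% cannot be excluded, and the possible loss is small and confined to one contrast.

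**What to change.** Keep the sample size. The sponsor should go back to the original calculation and revise section 5.1 to state:

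- the fold change used;
- the scale of the variability inputs (CV, SD or variance) and how depth was entered;
- power for each contrast at its planned group sizes, described as per gene before false discovery rate correction.

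If the original run used CVs at 1.5-fold, the text would read about 85% for WM versus normal MR, 90% for BGT versus normal MR and 90% for adverse versus normal outcome. Alternatively, it could give 1.55-fold as the change detectable with 90% power for WM. If the run used something else, those values should be printed instead. The 1.5-fold and 85% figures should not be inserted unchecked.

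The cost is a change of wording. One stated power may become slightly less favourable.

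### The 90% power in section 5.1 is set at an unadjusted type I error of 0.05 with no fold change stated, so it does not describe the Benjamini-Hochberg analysis planned in section 5

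*Protocol*

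**What the plan says.** Protocol section 5.1 gives the total and the software as "A total sample size of 272 patients (R (v3.3.1) and RNASeqPower (v1.12.0"), and the groups as "108 babies with WM injury, 82 with BGT injury, 82 with normal MR scans and 136 babies with adverse outcome". The error rates are "Type I error rate of 0.05 and Type II error rate of 0.1 (90% power"). The variability input for the outcome comparison is "Variance of 1.01 between encephalopathic babies with adverse outcomes and those with a normal outcome". For the white matter comparison the entry reads "Variance of 0.9 between encephalopathic babies with normal MR scans and those with WM injury". For the third comparison the figure given is "0.78 between encephalopathic babies with normal MR scans and those with basal ganglia injury". The sequencing depth is at least 30 million reads. The section names no fold change, FDR level, number of transcripts, expected share of changed transcripts or adjusted alpha.

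Section 5 describes the analysis: "we will fit linear regression models and calculate moderated t statistics for each transcript". On multiplicity, the same section says: "The p values will be corrected for multiple testing using the Benjamini-Hochberg false discovery rate method to control for type I errors". The diagnostic signature is then selected from the transcripts that come through this step as significant.

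**The concern.** A power figure has meaning only for a given decision rule and effect size. Section 5.1 uses a raw threshold of 0.05. Section 5 uses Benjamini-Hochberg, whose effective per-transcript threshold depends on how many transcripts are truly changed and is usually far below 0.05. For the same effect and the same babies, power is then lower than stated. With no fold change given, a reader also cannot tell which effect the 90% refers to.

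This bears on the primary aim, which relates gene expression to MR injury and to neurodisability. A short or empty list of transcripts could be taken as good evidence of no difference on the strength of the stated 90%. Transcripts lost at the FDR filter are also lost to the signature, since only significant transcripts go forward.

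**Working it through.** **Inputs from section 5.1.** Variability 1.01 (outcome), 0.9 (WM), 0.78 (BGT); depth 30 million reads; alpha 0.05; power 0.90; groups 136 adverse (leaving 272 − 136 = 136 without), 108 WM, 82 BGT, 82 normal MR.

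**Assumed or inferred.** Alpha two-sided; the stated variances used as coefficients of variation (CV); depth entered as 30; fold change 1.5 (back-solved); FDR level q; share π of transcripts truly changed; the same effect and CV for every changed transcript; independent tests.

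**Step 1: reproduce the stated sizes.** The RNASeqPower formula is

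n per group = 2(z₁₋α/₂ + z₀.₉)² × (1/depth + CV²) / (ln FC)²

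At α = 0.05, 2(1.960 + 1.282)² = 21.015, and (ln 1.5)² = 0.1644.

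- Outcome: 21.015 × (0.0333 + 1.0201) / 0.1644 = 134.7 (stated 136)
- WM: 21.015 × (0.0333 + 0.8100) / 0.1644 = 107.8 (stated 108)
- BGT: 21.015 × (0.0333 + 0.6084) / 0.1644 = 82.0 (stated 82)

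Solving each stated size for the fold change gives 1.497, 1.499 and 1.500. One-sided 0.05 gives 109.8, 87.9 and 66.9. Treating the inputs as true variances gives 133.4, 119.3 and 104.0. Neither variant fits.

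**Step 2: power at unadjusted 0.05 with the actual groups.** The noncentrality is δ = ln 1.5 / √[(1/30 + CV²)(1/n₁ + 1/n₂)], and power = Φ(δ − 1.960).

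- Outcome, 136 vs 136: δ = 3.258, power 90%
- BGT vs normal, 82 vs 82: δ = 3.241, power 90%
- WM vs normal, 108 vs 82: δ = 3.014, power 85%

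The WM size assumes 108 in each group, but only 82 babies are expected to have normal scans.

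**Step 3: power under Benjamini-Hochberg.** The effective threshold α* solves

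α* = q[(1 − π)α* + π × power(α*)], with power(α*) = Φ(δ − z₁₋α*/₂)

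At q = 5% and a 1.5-fold change:

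| Share changed | Outcome: α*, power | BGT: α*, power | WM: α*, power |
|---|---|---|---|
| 1% | 0.00016, 30% | 0.00015, 29% | 0.00010, 19% |
| 5% | 0.0014, 52% | 0.0014, 51% | 0.0010, 40% |
| 10% | 0.0033, 62% | 0.0032, 62% | 0.0026, 50% |

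A simulation of Benjamini-Hochberg on 20,000 independent transcripts, at the nominal δ of 3.242, gave 29%, 51% and 62% for the same three shares.

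**Step 4: sensitivity to the unstated inputs.** Outcome comparison, 1.5-fold:

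| Share changed | q = 5% | q = 10% |
|---|---|---|
| 0.1% | 10% | 15% |
| 1% | 30% | 40% |
| 5% | 52% | 63% |
| 10% | 62% | 73% |
| 20% | 72% | 81% |
| 50% | 83% | 90% |

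The last cell is 89.9% before rounding, against 90.3% at unadjusted 0.05.

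**Step 5: effect detectable with 90% average power.** At q = 5% and 5% changed, setting power to 0.9 gives α* = 0.05 × 0.05 × 0.9 / (1 − 0.05 × 0.95) = 0.00236. The fold change needed is 1.71 (outcome), 1.72 (BGT) and 1.79 (WM).

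**The case against.** The strongest objection is that the group sizes cannot identify alpha. In the formula, alpha and fold change enter as one common multiplier, so other pairs return the same three sizes: 1.6-fold at 0.0133, 1.7-fold at 0.0031, 1.75-fold at 0.0014, or 2.0-fold at about 0.00002. The groups also follow roughly from the assumed shares: 40%, 30% and 50% of 272 are 108.8, 81.6 and 136. This stands. A reader might infer that the sizes arise only at a per-transcript 0.05, and they do not show that. But section 5.1 itself states 0.05, and any other pair contradicts it. The 1.5-fold value remains an inference.

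Second, any power figure under Benjamini-Hochberg needs an FDR level, a share of changed transcripts and a fold change, and the protocol gives none of them. This also stands, and it means the figures above are conditional. The FDR level may properly sit in a statistical analysis plan that is not at hand. That does not repair a 90% already stated in the protocol on a different error rate.

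Third, this is an observational cohort whose summary speaks of feasibility, and nothing in its conduct would change. That is fair as a measure of consequence, and it is why the remedy is confined to restating the power. The misreading of a short list is a risk, not something the protocol says will happen.

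**Conclusion.** The point holds: the stated 90% does not apply to the planned analysis, and the effect it refers to is not given. For the inferred 1.5-fold change, power was below the stated 90% in every scenario tried at FDR 5% or 10%. It came within rounding of 90% only for the outcome and BGT comparisons, at FDR 10% with half of all transcripts changed. WM versus normal is weakest throughout, and falls short at about 85% even without correction.

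A reader might infer that the real power is about 30–65%. The documents do not support that as an unconditional figure. It corresponds to FDR 5% with roughly 1–12% of transcripts changed, for the outcome and BGT comparisons only. Over 0.1–50% changed, the outcome figure runs from about 10% to 83% at FDR 5% and from about 15% to 90% at FDR 10%.

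Nor is this a calculation error: the stated sizes reproduce closely. The fault is that the error rate used for sizing is not the one used for inference.

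All power figures rest on the inferred fold change, the CV and depth readings, a common effect across changed transcripts, and independent tests.

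**What to change.** Keep the sample size and the analysis. In section 5.1, replace item (iv) with the fold change, the FDR level, the assumed share of changed transcripts, the resulting per-transcript alpha, and the average power for each comparison at its actual group sizes, including 108 versus 82 for WM. These should come from the sponsor's own preliminary data, with a short range for the share changed. State also whether the variability inputs are variances or coefficients of variation.

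Give each comparison its own figure. At FDR 5% with 5% changed, for illustration, 90% average power is reached at about 1.71–1.72-fold for outcome and BGT but only at about 1.79-fold for WM, so one sentence quoting 1.7-fold for all three would be wrong.

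The cost is a recalculation and a rewritten paragraph. No babies are added, and the stated power becomes less favourable.
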